7.2 Rationale

The steroid-converting enzyme, 11 β -hydroxysteroid dehydrogenase Type 1 (11 β -HSD1), is found predominantly in the liver, adipose and brain. It catalyses the reduction of inert cortisone to the active glucocorticoid hormone, cortisol. There is comprehensive evidence from studies in rodents and in humans that regulation of cortisol levels via inhibition of 11 β -HSD1 provides a therapeutic strategy to treat metabolic diseases such as Type 2 diabetes and central nervous system (CNS) conditions such as cognitive impairment and AD^{7,8,9,10,11}.

In the brain, 11 β -HSD1 is highly expressed in regions such as the hippocampus, frontal cortex and cerebellum. These regions are important for cognition and the hippocampus, in particular, has high expression of glucocorticoid receptors. There is substantial evidence that elevated glucocorticoid levels contribute to cognitive dysfunction, are neurotoxic and may contribute to AD^{12,13,14,15}.

For example:

- In vivo, in rats, corticosterone administration causes regression of hippocampal neuronal dendrites¹⁶.
- In primates, long-term (1 year) implantation of cortisol pellets in the hippocampus causes shrinkage and dendritic atrophy¹³. 11 β -HSD1 knock-out mice are protected against glucocorticoid-associated, age-related cognitive dysfunction on two different genetic backgrounds^{17,18}. Long-term potentiation (the probable cellular/synaptic electrophysiological basis of memory) is enhanced in hippocampal slices from these mice.
- In three separate and independent studies pharmacological inhibition of 11 β -HSD1 leads to improvements in cognition in wild-type aged and young rodents and in the Tg2576 model of AD^{9,10,11}.
- In rodent models of AD, corticosterone is elevated, whilst treatment with glucocorticoids has been shown to elevate A β ¹⁵.
- Studies from the University of Edinburgh found that the 11 β -HSD1 enzyme amplified glucocorticoid production in target tissues (such as adipose and the hippocampus). Overexpression of the gene in adipose resulted in obesity whilst genetic deletion of the gene protected against age-related memory impairment, leading to the hypothesis that inhibitors of 11 β -HSD1 could have the potential to treat metabolic disease and cognitive impairment by safely reducing glucocorticoid levels in these target tissues. The original proof-of-concept studies in humans at the University of Edinburgh utilised the prototype, non-selective, 11 β -HSD1 inhibitor carbenoxolone, which significantly improved

cognition in healthy elderly men and in subjects with Type 2 diabetes by significantly ($p < 0.01$) improving verbal fluency and memory at 4 to 6 weeks compared to placebo¹⁹.

Reducing glucocorticoid action in the CNS has therefore emerged as an important therapeutic goal in the treatment of age-associated cognitive impairment and AD.

Xanamem™ (former designation UE2343) is a new investigational medicinal product, under development for the treatment of mild AD with the potential for both symptomatic and disease-modifying effects. Xanamem™ displays high potency and selectivity for human 11 β -HSD1 when compared to related hydroxysteroid dehydrogenase enzymes and receptors. Based on pre-clinical data from rodent models of AD and age-related cognitive impairment it is anticipated that Xanamem™ will have a beneficial effect on the cognitive decline associated with AD. Additionally, pre-clinical data also indicate that treatment may slow the progression of β -amyloid plaque deposition in the brain.

Two Phase I studies (RD 656/25368 [a Single Ascending Dose study] and ACW0001 [a Multiple Ascending Dose, Fed-Fasted and CNS study]) in 88 healthy volunteers established the pharmacokinetic (PK) and pharmacodynamic (PD) parameters of Xanamem™ and concluded that the drug was safe and well tolerated in doses from 2 to 35 mg twice daily, and that it should preferably be taken with food. The presence of the drug in the cerebrospinal fluid (CSF) confirmed that it crosses the blood brain barrier. PK/PD modelling of the CSF to plasma ratios obtained in the multiple ascending dose study were used to select the optimum dose regimen for this Phase II study in mild AD.

This Phase II study will assess the safety, tolerability and efficacy of oral Xanamem™ for 12 weeks in male and female subjects aged 50 years and older with mild dementia due to AD. This study will be conducted in compliance with the protocol, International Conference on Harmonisation (ICH) guidelines on Good Clinical Practice (GCP) and applicable local regulatory requirements and laws.

In this study design, subjects will be randomised to receive either 10 mg once a day (QD) Xanamem™ or matching placebo for a 12-week period.

To support the selection of this dose, PK modelling was conducted based on the Multiple Ascending Dose (MAD) study results obtained from human volunteers, when 10, 20 and 35 mg of Xanamem™ was administered twice daily for 10 days. From this modelling, predicted PK values in plasma for maximum concentration (C_{max}), minimum concentration (C_{min}) and area under the plasma concentration-time curve from 0 to 24 hours (AUC_{0-24hr}) and for CSF C_{max} , C_{min} were estimated at steady state for 10, 20 and 30 mg Xanamem™ administered QD. This modelling confirmed that any of these doses would achieve consistent Xanamem CSF levels above the inhibitory concentration of 50% (IC_{50}) (the optimal target threshold) for the 11 β -HSD1 enzyme.

More information can be found in the Investigator's Brochure²⁰.

8 STUDY OBJECTIVES

8.1 Primary Objectives

The primary objective of the study is to evaluate the extent to which Xanamem™ improves performance from Baseline to end of treatment (EOT) compared to placebo, as measured by changes in AD COMposite Scores (ADCOMs, composite data derived from Alzheimer's Disease Assessment Scales - Cognitive subscale version 14 [ADAS-Cog v14], Clinical Dementia Rating Scale - Sum of Boxes [CDR-SOB], and Mini-Mental Status Examination [MMSE]) and ADAS-Cog v14 as primary endpoints in subjects with mild dementia due to probable AD.

8.2 Secondary Objectives

Secondary objectives of this study are to assess the extent to which Xanamem™ will improve performance from Baseline to EOT compared to placebo, as measured by changes to:

- Rey Auditory Verbal Learning Test (RAVLT)
- CDR-SOB
- MMSE
- Neuropsychiatric Inventory (NPI)
- Neuropsychological Test Batteries (NTB) – Executive Domain

8.3 Efficacy Assessments

See [Section 11.1](#) for details of the efficacy assessments.

- ADAS-Cog v14
- RAVLT
- CDR-SOB
- MMSE
- NPI
- NTB – Executive Domain (Controlled Word Association Test [COWAT] and Category Fluency Test [CFT])

ADCOMs-related assessments (ADAS-Cog v14, CDR-SOB and MMSE), RAVLT, NPI and NTB – Executive Domain, will be performed at the Baseline (Week 0) and the EOT (Week 12) visits to minimise burden for rater and subject.

MMSE and CDR-SOB will also be performed at Screening.

8.4 Safety Assessments

- Change in clinical safety laboratory values from Baseline (Week 0) to EOT (Week 12)
- Incidence of adverse events (AEs)

- Electrocardiogram (ECG) (study sites' local equipment will be used and ECG will be read locally by an appropriately qualified and experienced ECG reader; the same equipment should be used throughout the study at that study site)
- Neuropathy Total Symptom Score (NTSS)-6: The six questions of NTSS-6 should be completed as part of the assessment of subjects' medical history, also asking for input from the caregiver to make sure no information is lost. Each item will also be graded for its frequency and intensity, adding up to a total score from "0" to "21.96" points. A total score of > 6 would exclude the subject from the study.
- The neurological examination will cover all aspects of the Toronto Clinical Neuropathy Score (TCNS). See [Section 12.5](#) for details of this examination.
- Nerve Function Monitoring (NFM). See [Section 12.7](#) for details of NFM.
- Columbia Suicide Severity Rating Scale (CSSRS)
- Physical Examination
- Vital signs

All evaluations will be performed as detailed in the Schedule of Assessments ([Table 1](#)). Ad hoc telephone contact may occur at any time-point throughout the study, if deemed necessary by the investigator/study nurse, or if the subject wishes to report an adverse event (AE).

8.5 Pharmacokinetics/Pharmacodynamics

- **PK assessment:** PK blood samples will be taken from all enrolled subjects.
- **Optional PD assessment:** PD blood samples will be taken from approximately 50 subjects enrolled into the main study who also volunteer to take part in the PD sub-study, unless a higher number is defined as a result of the analysis of the PD data, by the Data Safety Monitoring Board (DSMB). Samples will be taken pre-dose from subjects in a fasted state, to evaluate the adrenocorticotrophic hormone (ACTH), dehydroepiandrosterone sulfate (DHEAS), androstenedione and testosterone at the Baseline (Week 0) visit, Interim visits (Week 4 and Week 8), EOT (Week 12) and Follow-up (4 weeks post last dose of study drug) visits. For optimal results, the sample for androstenedione analysis should be taken between 6 am and 10 am.

Note: results of the PK and PD (biomarkers) analyses will not be disclosed to study sites to avoid unintended subject treatment unblinding (for further details refer to the XanADu Laboratory Manual).

8.6 Other Exploratory Assessments

- **Metabolic function** (lipids, blood pressure, glucose, haemoglobin A1c [HbA1c], body weight, body mass index [BMI]) analysis will be performed on all enrolled subjects.

9 INVESTIGATIONAL PLAN

9.1 Overall Study Design and Plan

9.1.1 Description

This is a Phase II, randomised, multi-centre, double-blind, placebo-controlled proof-of-concept study to assess the safety, tolerability and efficacy of oral Xanamem™ QD in adult subjects with mild dementia due to AD.

It is planned to randomise approximately 174 subjects at approximately 20 study sites in three countries (Australia, UK, and USA), with the aim to enrol 7 to 10 subjects at each study site. Subject enrolment will be competitive but a cap of 20 subjects per study site is to be established to avoid any site effects. In case data quality at one study site is creating concerns, an enrolment stop can also occur at fewer than 20 subjects.

The DSMB will periodically meet for the review of accumulating safety study data and will also be involved in the interim efficacy analysis (see [Section 15.2.4](#) for details).

At the Baseline visit (Week 0), eligible subjects will be randomised on a 1:1 ratio to receive either Xanamem™ administered orally, QD (treatment group) or matching placebo (placebo group). Subjects will return to the study site for the Interim visits (Week 4 and Week 8), EOT (Week 12) and Follow-up (4 weeks post last dose of study drug) visits, at which study assessments, as detailed in [Table 1](#) (Schedule of Assessments), will be performed. For further details on the dosing and treatment of subjects, refer to [Section 10](#).

Ad hoc telephone contact may occur at any time-point throughout the study, if deemed necessary by the investigator/study nurse, or if the subject wishes to report an AE.

Subjects will be interviewed and examined at the study site at each visit, and will complete a variety of questionnaires and routine safety evaluations.

Selected subjects will undergo additional PD sampling at specific visits after providing appropriate informed consent. Subjects who do not provide consent for this optional assessment, will still be eligible for the main study.

The overall study duration for an individual subject will be 17 to 20 weeks, including a screening period of 1 to 4 weeks, a double-blind treatment period of 12 weeks, and a follow-up period of 4 weeks. The total duration of the study is expected to be approximately 2 years (last subject last visit).

9.2 Discussion of Study Design

This study is designed to investigate the safety, tolerability and efficacy of Xanamem™ in subjects with mild dementia due to AD.

Based on Xanamem™'s mode of action on the hippocampal function, amnesic symptoms may respond best, thus favouring the inclusion of mild dementia due to AD, with given evidence of disease progression. Subjects will be treated in a double-blind fashion, where both the investigators and subjects will be unaware of the treatment assignments, to minimise any subjective or unrecognised bias carried by the investigators and subjects. Placebo will be

used as the comparator in this study. In this study, Xanamem™ will be administered in conjunction with current standard therapy (see [Sections 9.3.1](#) and [9.3.2](#)).

Recognising that no animal toxicology reproductive or development studies have been performed with Xanamem™ as yet, women of childbearing potential (WOCBP) who have a positive pregnancy test at Screening and/or Baseline, or those who are not willing to use highly effective methods of contraception or who are not permanently sterile or have not had a hysterectomy, bilateral salpingectomy or bilateral oophorectomy, will be excluded from the study.

Subjects should aim to take the study drug at the same time each morning with meals (i.e. not in fasted condition) due to an approximately 25% higher bioavailability observed when taken in a fed state. Drug intake when fasted has no safety concern and will not be treated as a protocol deviation.

A variety of scales will be employed in this study for the assessment of efficacy. ADCOMs (composite data derived from ADAS-Cog v14, CDR-SOB and MMSE) are used to determine the primary efficacy endpoint as these scales have a higher sensitivity for domains affected by early AD and episodic memory problems than other scales²¹. ADAS-Cog will be a co-primary endpoint since this is the most established and widely validated scale. RAVLT is used to determine the most important secondary efficacy endpoint as this scale has the highest expected sensitivity for change in episodic memory, which is the most probable target of Xanamem™ effects. Although many scales will be employed during this study, subjects will not complete all of them at every visit. This is to ensure no learning effect between two adjacent visits, to reduce the total number of assessments, to minimise burden for raters and subjects and thus increase study compliance and to allow more focus on critical parameters.

Sparse PK blood samples will be taken from all subjects who participate in the main study. The PK samples will be taken pre-dose and between 3 and 5 hours post-dose (as required per [Table 1](#)), i.e. the time interval during which peak concentrations were observed in the Phase I studies. In addition, a PK sample will be collected from each subject in whom a serious AE (SAE) occurs, noting the time of the last dose of study drug administered relative to the time at which the PK sample was collected.

PD blood samples will be collected from a sub-group of approximately 50 subjects (unless a higher number is defined as a result of the DSMB analysis of the PD data). The PD sampling in this study will complement the previously reported Phase I data, in which most of the subjects were male and only a small number of subjects were aged 50 years or older. If, after evaluation of the PD data by the DSMB, it is considered that an insufficient number of subjects are on active drug, further PD data will be collected.

NFM, including vibration detection threshold, thermal (cold and warm) detection, and nerve conduction, is required to rule out any impact of Xanamem™ on nerve conduction in an elderly population, and to exclude long-term neurotoxic effects. Subjects with clinically symptomatic peripheral nerve damage at the Screening visit (e.g. polyneuropathy) will be excluded from the study to avoid confusion with the Xanamem™ safety profile.

Other efficacy/safety endpoints used in this study are well-established and well-accepted measurements for AD studies.

Interim visits are scheduled at Week 4 and Week 8 to allow the observation of potential adverse reactions.

9.2.1 Dose Rationale

In this study design, subjects will be randomised to receive either 10 mg QD Xanamem™ or matching placebo for a 12-week period.

To support the selection of this dose, PK modelling was conducted based on the MAD study results obtained from human volunteers, when 10, 20 and 35 mg of Xanamem™ was administered twice daily for 10 days. From this modelling, predicted PK values in plasma for C_{max} , C_{min} and AUC_{0-24hr} and for CSF C_{max} , C_{min} were estimated at steady state for 10, 20 and 30 mg Xanamem™ administered QD. This modelling confirmed that any of these doses would achieve consistent Xanamem CSF levels above the IC_{50} (the optimal target threshold) for the 11β -HSD1 enzyme.

More information on the dose recommendation can be found in the Investigator's Brochure²⁰.

9.2.2 Risk/Benefit and Ethical Assessment

Xanamem™'s mechanism of action suggests a main role on hippocampal function, which may improve amnesic symptoms that are the main symptoms in subjects of mild AD. Furthermore, Xanamem™ may slow the progression of amyloid plaque deposition in the brain. Therefore, Xanamem™ has the potential for both symptomatic and disease-modifying effects in subject with mild AD.

Xanamem™ is an inhibitor of the 11β -HSD1 enzyme. Compounds which inhibit 11β -HSD1 are intended to affect the intracellular cortisone-cortisol balance, resulting in altered glucocorticoid action. It is therefore expected that AEs seen following the administration of Xanamem™ may be related to effects on glucose and fatty acid metabolism, or loss of suppression of innate immunity. In addition, inhibition of 11β -HSD1 results in enhanced cortisol clearance and potentially a compensatory increase in ACTH and cortisol secretion to maintain normal cortisol levels. As a result, ACTH-dependent secretion of adrenal androgens may be increased.

To date, Xanamem™ has an acceptable safety profile: in the MAD study²², all treatment-emergent AEs (TEAEs) were either mild or moderate in intensity. A total of 6/24 (25.0%) subjects reported at least one TEAE possibly related to study drug, whilst all the other TEAEs were reported as unrelated or unlikely to be related to study drug.

Of the five TEAEs considered to be moderate in intensity, one event of diarrhoea (20 mg UE2343) and one event of headache (35 mg UE2343) were considered as possibly related to study drug. The other moderate TEAEs were all unrelated or unlikely to be related to study drug. The laboratory parameters were within normal range and no clinically significant abnormalities were recorded. In the subsequent fed-fasted study²² in 12 subjects, the most commonly reported TEAE by preferred term was "Abnormal dreams", with a total of

five events reported by 5/12 (41.7%) subjects. These were considered possibly related to study drug (two events under fed conditions, one under fasted conditions and two across both the fed and fasted period), all mild in intensity and resolved.

Overall, there were no clinically significant abnormalities noted in nerve conduction studies for any of the subjects in the MAD cohorts.

Post-study, a total of six subjects experienced QT time increases of > 30 msec from Baseline using the Bazett's correction (QTcB). QTcB increases of > 60 msec were reported on one subject in the placebo group (change from Baseline to Day 10 [4 hours post-dose]) and one subject in the 20 mg Xanamem™ group (change from Baseline to post-study).

The potential benefits of Xanamem™ are therefore considered to outweigh the potential risks.

Close monitoring of safety, including potential effect on metabolic and nerve function, will be conducted throughout this study.

9.3 Selection of Study Population

9.3.1 Inclusion Criteria

A subject will be eligible for enrolment in the study if ALL of the following criteria apply:

1. Males and females aged 50 years or older at the time of informed consent.
2. Female subjects:
 - a) Post-menopausal women, defined as no menses for 12 months without an alternative medical cause. If there is any concern about the menopausal status of a prospective female subject, a follicle-stimulating hormone (FSH) test should be requested to confirm post-menopausal status. Post-menopausal women confirmed by FSH level > 40 mIU/mL, will be confirmed by central laboratory.
 - b) WOCBP must have a negative pregnancy test at Screening and Baseline, and be willing to use highly effective methods of contraception from the Screening visit until 3 months after last dose of study drug. The central laboratory will flag positive serum human chorionic gonadotropin as exclusionary at Screening (re-test of Screening if required). In such cases, the site will perform a local urine pregnancy test at Baseline to determine if the subject can continue to randomisation (see [Appendix IV](#) for more information).
 - c) Are permanently sterile or have had a hysterectomy, bilateral salpingectomy or bilateral oophorectomy.
 - d) Women must not be breastfeeding.
3. Male subjects:
 - a) Who are sexually active, fertile men must use highly effective methods of contraception from Day 1 until 3 months after last dose of study drug if their partners are WOCBP (see [Appendix IV](#) for more information).
 - b) Who are permanently sterile or have had bilateral orchiectomy.

4. Diagnosis of mild dementia due to probable AD with increased level of certainty (provided by evidence of clinical deterioration within the 6 months preceding Screening, as assessed by the investigator) as determined by the National Institute of Ageing (NIA) and the Alzheimer's Association (AA) workgroup, detailed in Section 4.1 and 4.2.1²³. Individual criteria will be included in the electronic case report form (eCRF).
5. Mild dementia due to probable AD with MMSE of 20 to 26 (inclusive).
6. CDR Global Score of 0.5 to 1.0.
7. A brain magnetic resonance imaging (MRI) or computed tomography (CT) scan in the 12 months preceding Screening (a wider window may be accepted but requires written approval by the ICON Medical Monitor [MM]) that, in the investigator's opinion, is consistent with AD as the principal aetiology of the dementia with no other clinically significant abnormality, e.g. another principal underlying aetiology of the subject's dementia, or a lesion which could affect cognition e.g. a brain tumour or large stroke.
8. On stable dose of acetylcholinesterase inhibitor (AChEI) and/or memantine (at least 3 months prior to Screening) OR treatment-naïve. Initiating AChEIs or memantine during the study will not be permitted.
9. Apart from a clinical diagnosis of mild dementia due to probable AD, the subject must be in good health as determined by the investigator, based on medical history and screening assessments.
10. Has a consenting study partner who, in the investigator's judgement, has frequent and sufficient contact with the subject to be able to provide accurate information as to the subject's cognitive and functional abilities. The study partner must be available to provide information to the investigator and study site staff about the subject and agrees to attend all study site visits in person for scale completion. A study partner should be available for the duration of the study. The measure of adequate availability will be at the investigator's discretion.
11. Must be willing and able to comply with the requirements of the protocol and must be available to complete the study.
12. Must satisfy a medical examiner about their fitness to participate in the study.
13. Must provide written informed consent to participate in the study.

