Diagnosis and Main Criteria for Inclusion: 
 1. Males and females aged 50 years or older at the time of informed consent. 2. Female subjects: 
 a) Post-menopausal women, defined as no menses for 12 months without an alternative medical cause. If there is any concern about the menopausal status of a prospective female subject, a follicle-stimulating hormone test (FSH) should be requested to confirm post-menopausal status. Post-menopausal women confirmed by FSH level > 40 mIU/mL, will be confirmed by central laboratory. b) Women of childbearing potential (WOCBP) must have a negative pregnancy test at Screening and Baseline, and be willing to use highly effective methods of contraception from the Screening visit 		

Name of Sponsor/Company: Actinogen Medical	Individual Study Table Referring to Part of the Dossier:	(For National Authority Use Only)
Name of Product: Xanamem™		
Name of Active Ingredient: (5-(1H-Pyrazol-4-yl)thiophen-3-yl)(3-hydroxy-3-(pyrimidin-2-yl)-8-azabicyclo[3.2.1]octan-8-yl)methanone	Volume: Page:	

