9.3.2 Exclusion Criteria

A subject will NOT be eligible for this study if ANY of the following criteria apply:

1. Clinically significant abnormalities in vital signs (blood pressure, heart rate, respiration rate and oral temperature), as determined by the investigator.
2. Clinically significant abnormal haematology, biochemistry and urine examination values, as determined by the investigator. Additionally, abnormal liver and renal function and Vitamin B12 levels below lower threshold may impact cognitive function. The following values will have an alert flag on the laboratory report and are specifically excluded:

- a) Vitamin B12 < 176 pg/mL
- b) Haemoglobin < 11 g/dL for females and < 12 g/dL for males
- c) Aspartate aminotransferase > 3 x upper limit of normal (ULN)
- d) Alanine aminotransferase > 3 x ULN
- e) Serum creatinine > 2 x ULN
- f) Urine benzodiazepines when positive: One re-test will be allowed in cases where the subject's intake of benzodiazepines is within the allowed dose. Re-tests must be performed within 7 days of the last benzodiazepine dose prior to the Baseline visit. A positive re-test for urine benzodiazepines is exclusionary.

Re-testing of laboratory parameters that requires a confirmatory value within the screening period will be permitted in an effort to find all possible well-qualified subjects. The most current result prior to randomisation is the value by which study inclusion will be assessed, as it represents the subject's most current, clinical state. Consultation with the ICON MM is advised, to identify whether repeat testing of any particular parameter is acceptable and clinically relevant.

3. Has had a significant systemic illness or infection within the past 4 weeks prior to randomisation, as determined by the investigator.
4. Clinically significant neurological disease other than AD, such as (but not limited to) Parkinson's disease, multi-infarct dementia, Huntington's disease, normal pressure hydrocephalus, brain tumour, progressive supranuclear palsy, seizure disorder, subdural haematoma, multiple sclerosis or a history of significant head trauma followed by persistent neurologic deficits or known structural brain abnormalities.
5. Subjects with clinical evidence of peripheral neuropathy or historical evidence of clinically significant nerve conduction abnormalities. Clinical evidence of neuropathy is defined as:

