- 7 One PK sample will be taken 3 to 5 hours post-dose at the Baseline (Week 0) visit and two PK samples will be taken (at arrival on site [pre-dose] and 3 to 5 hours post-dose) at the Interim visits (Week 4 and Week 8). One PK sample will be taken at the EOT (Week 12) visit. NB: The subject will not be dosed during the EOT visit. For details, see [Section 9.4.1](#). The exact time-points of blood sampling for PK analysis and drug intake will be documented. Between visits, subjects will record the exact times of study drug intake in the Drug Intake Diary. The subject will be required to bring the diary to the Interim visits (Week 4 and Week 8) and EOT (Week 12) visit.
- 8 Taken from the blood sample at Baseline (Week 0), and EOT (Week 12) visits.
- 9 Women of childbearing potential only. A serum pregnancy test will be performed at Screening and a urine pregnancy test at all subsequent clinic visits.
- 10 Females only. To be taken only if there is clinical concern about the subject's menopausal status.
- 11 Urine collected for the urinalysis sample will also be used to test for the presence of benzodiazepines at the Screening visit. A second urine sample, prior to randomisation, will be needed if a benzodiazepine re-test is required.
- 12 This sample should be collected as soon as possible after the subject arrives at the study site (pre-dose). This could, if possible, be combined with other blood draws to minimise the burden for subjects. For optimal results, the sample for androstenedione analysis should be taken between 6 am and 10 am.
- 13 ECG at Baseline only required if Screening ECG was performed more than 2 weeks earlier.
- 14 Ad hoc telephone contact may occur at any time-point throughout the study, if deemed necessary by the investigator/study nurse, or if the subject wishes to report an AE. If an SAE occurs in a subject, the subject will return to the site for a PK sample. Additional procedures will be performed as indicated, for details see [Section 12.1.1.3](#)).
- 15 Cortisol will be measured using the existing PK blood samples taken at Baseline (Week 0), Week 4, Week 8, and Week 12.

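### Inclusion criterion 2b and section 9.2 exclude a woman of childbearing potential with a positive Screening serum hCG, but the last sentence of 2b appears to let a negative Baseline urine test admit her

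*Protocol*

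**What the plan says.** Criterion 2b in Protocol section 9.3.1 has three sentences that matter here.

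- Sentence 1: "WOCBP must have a negative pregnancy test at Screening and Baseline". It also requires highly effective contraception.
- Sentence 2: "The central laboratory will flag positive serum human chorionic gonadotropin as exclusionary at Screening (re-test of Screening if required".
- Sentence 3: "In such cases, the site will perform a local urine pregnancy test at Baseline to determine if the subject can continue to randomisation".

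The synopsis (section 4) carries the same three sentences, beginning "Women of childbearing potential (WOCBP) must have a negative pregnancy test at Screening and Baseline".

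Section 9.2 lists among those to be excluded "women of childbearing potential (WOCBP) who have a positive pregnancy test at Screening and/or Baseline". Its reason is that no animal reproductive or developmental toxicology studies have yet been done with the drug.

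On the test schedule, Table 1 footnote 9 (section 9.4) says: "A serum pregnancy test will be performed at Screening and a urine pregnancy test at all subsequent clinic visits".

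**The concern.** Sentence 1 of 2b and section 9.2 each make a positive Screening test disqualifying. Sentence 3 takes up exactly the women whose Screening serum was flagged and passes the decision to a different, local test at Baseline. Two sites acting in good faith could reach opposite decisions on the same woman.

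What is at stake is exposure of a possible pregnancy to a drug that has no reproductive toxicology data. A site following sentence 3 could randomise and dose a woman whose positive serum result has not been explained. The next scheduled pregnancy test after Baseline is at Week 4.

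**Working it through.** No arithmetic applies, and the plan states no figure on this point. The check is to apply each rule to each combination of Screening serum and Baseline urine result. A positive serum result here means one that no Screening re-test has reversed.

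| Screening serum | Baseline urine | 2b sentence 1 | Section 9.2 | 2b sentence 3, natural reading |
|---|---|---|---|---|
| Negative | Negative | Eligible | Eligible | Does not apply |
| Negative | Positive | Excluded | Excluded | Does not apply |
| Positive | Positive | Excluded | Excluded | Excluded |
| Positive | Negative | Excluded | Excluded | May continue to randomisation |

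Only the last row gives conflicting answers. The table shows where the text conflicts; it says nothing about how often that row occurs.

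The next step is to see whether other text settles that row.

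1. **The Screening re-test in sentence 2.** A re-test could clear a false positive. The sentence does not name the specimen or say that a negative re-test is needed, and sentence 3 then gives the decision to the Baseline urine test.
2. **The re-test rule under exclusion criterion 2 (section 9.3.2).** It says "Re-testing of laboratory parameters that requires a confirmatory value within the screening period will be permitted" and "The most current result prior to randomisation is the value by which study inclusion will be assessed". Appendix II lists hCG under biochemistry, so the rule arguably reaches a repeat serum hCG. But it concerns repeats within the screening period, and it does not amend 2b or section 9.2.
3. **Re-screening (section 9.4.1.1).** A subject re-screened within 30 days repeats the assessments that would exclude her. Nothing there substitutes a different test.
4. **The Medical Monitor (sections 9.3.2 and 9.4.1.1).** Sites may ask about eligibility and repeat testing. That is a route to an answer, but the protocol gives the Monitor no rule to apply.
5. **Appendix IV.** Criterion 2b refers to it, but it covers fertility definitions and contraception and says nothing about discordant tests.

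None of the five decides which sentence governs. By contrast, exclusion criterion 2f on urine benzodiazepines gives the number of re-tests, their timing, the test to repeat and the consequence of a second positive.

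**The case against.** The best defence reads 2b as a sequence: flag the positive serum, re-test it, then apply the Baseline urine test as a further gate. If the re-test is negative, sentence 1 is met at Screening and the urine test settles Baseline. If serum stays positive, she fails sentence 1, because section 9.3.1 requires all criteria to apply and section 9.4.1.2 requires continued eligibility before randomisation. Sentence 3 does not say outright that a negative urine result cures a failed Screening test. This reading is possible but less natural, because sentence 3 follows directly from the positive serum flag and speaks of the urine test as deciding whether she continues.

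A second defence is that sentence 3 is a specific exception and should prevail over general text, particularly over a discussion section such as 9.2. That gives sites an answer, but it leaves section 9.2 saying the opposite, so the text would still need aligning.

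Part of the objection stands. Since footnote 9 already gives every WOCBP a urine test at Baseline, a reader might infer that sentence 3 can have no purpose except to let urine override serum. The documents do not support that inference: the sentence could simply restate the scheduled test as a local gate before randomisation. A reader might also infer that pregnant women are likely to be dosed. That is not supported either. It would take a WOCBP aged 50 or older, a positive serum result that no re-test reversed, a site that relied on sentence 3, and a falsely negative urine result normally at least 7 days after Screening. Exposure to active drug would further depend on the 1:1 allocation. Confirmed pregnancy leads to withdrawal under section 9.5.

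**Conclusion.** The criterion is wrong as written, and the error is minor. For one group, serum-positive and urine-negative WOCBP, the protocol can be followed to exclusion or to randomisation. The conclusion rests on the natural reading of sentence 3. On the sequential reading the rule is consistent but poorly expressed, and the same rewording cures it.

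The size cannot be given as a number, because the documents report no expected count of WOCBP and no rate of discordant tests. With entry at age 50 or older, I assume it is very few. The matter is one of patient safety alone; the efficacy analyses, power and type I error do not depend on it. It merits correction because the exclusion exists precisely for want of reproductive toxicology data and the edit is cheap.

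**What to change.** State one rule in the same words in criterion 2b, section 9.2 and the synopsis:

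- a positive Screening serum hCG excludes the subject unless a repeat serum test before randomisation is negative; and
- a negative Baseline urine test is required in addition and does not override an unresolved positive serum result.

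This still gives a false-positive serum result a way back in. The cost is an edit in three places, an occasional repeat serum test that must fit the 28-day screening limit in section 9.4.1.1, and exclusion of the rare woman whose serum hCG stays positive without pregnancy. Sentence 3 may have been meant to admit her. If the sponsor does intend that, sentence 1 of 2b and section 9.2 (and the synopsis with them) should instead state the exception and the confirmation that pregnancy has been ruled out.
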